#### Clinical outcome measures

The Brief Pain Inventory is a composite self-report measure comprising a pain intensity subscale (4 items; current, least, worst, and average pain rated on 0-10 scale) and a pain-related functional interference subscale (7 items assessing interference with general activity, walking, sleep, work, mood, enjoyment of life and relationships rated on 0-10 scale). The BPI is a recommended outcome measure in chronic pain trials and is validated in primary care populations.

BPI total score and opioid use, expressed as daily morphine equivalent dose, are proposed as the co-primary outcomes for a future main trial. This reflects the importance to patients, confirmed by PPIE, that pain and pain-related interference does not increase when reducing opioids.

In this study we will explore the feasibility of calculating average daily morphine equivalent dose (MED) using participant self-reported data about opioid use over the preceding 4 weeks, and using prescribing data from electronic medical records. A pain medicines use questionnaire will collect data on dose, dosing regimen (regular or as required) and frequency of use for each opioid and non-opioid pain medicine used. Morphine equivalent doses will be calculated for each opioid medicine prescribed using published conversion factors.

A medication-related side-effects checklist will collect information about common opioid-related side-effects (constipation, itching, daytime sleepiness, dry mouth, nausea, vomiting, dizziness, headache, confusion, difficulty concentrating) and their severity on a 5-point scale.

Pain-related self-efficacy will be measured using the Pain Self-Efficacy Questionnaire (PSEQ), a 10-item questionnaire, assessing the confidence of people with any type of chronic pain to cope with pain in general, to perform a range of specific activities despite pain and their confidence to cope with pain without medication. Each item is rated on a 0-6 scale, with higher scores reflecting stronger self-efficacy beliefs.

#### Health economic evaluation

The EQ-5D-5L is a generic measure of health related quality of life that provides a single index value for health status that will allow calculation of Quality-Adjusted Life Years (QALYs) in the health economic evaluation nested in a proposed future main trial. Respondents rate their degree of impairment in five health domains (mobility, self-care, usual activities, pain/discomfort, anxiety/depression) on a 5-point scale (no problems, slight problems, moderate problems, severe problems and extreme problems).

A patient self-report questionnaire (developed for the study) will be used to collect relevant healthcare resource use data, including the use of NHS and private health care, over the counter purchases and information on both time off work and presenteeism. The focus will be on persistent pain-related healthcare resource use and healthcare resource use due to opioid-related side effects. Questions will request information regarding primary care visits, visits to other health care professionals, tests and investigations, opioid prescriptions, treatment (e.g. injections), secondary care consultations, inpatient stays and surgery during the previous 3

months. Data on broader health care costs will also be collected, related to out of pocket costs (e.g. over the counter medications such as laxatives) and private health care. Information on time off work, occupation, typical work activities and the nature of their employment (full time or part time) will also be requested and the Single-Item Presenteeism Question from the Work Productivity and Activity Impairment Questionnaire will be used to estimate presenteeism.

Preliminary resource use data will also be collected regarding delivery of the PROMPPT intervention, including clinical pharmacist appointments (face to face and telephone) and GP input, to refine data collection processes in a future main trial. Opioid prescription information will also be available through medical record review (see 5.3.3).

#### 5.3.2 Nested Process Evaluation

#### **Observed Consultations**

A sample of approximately 10% of consultations (aiming for n=2 per practice) will be observed (by a researcher and/or digitally audio-recorded) with clinical pharmacist and participant consent. Data from these observed consultations will be collected to allow assessment of key aspects of intervention delivery: treatment differentiation, (Did the clinical pharmacists only deliver PROMPPT and not other treatments?), treatment competency (Did Clinical Pharmacists maintain the skills learned in training?), and treatment delivery (Were PROMPPT components delivered as intended?).

### Case report forms (CRF)

The clinical pharmacists will be required to complete a CRF for each participant. An e-CRF will be embedded within the practice electronic medical record. Following completion this can be embedded into the individual participants' medical record. The CRF will collect information on what happened during the PROMPPT interventions (e.g. discussion of the Pain Concerns Form, discussion of the patient perspective on making changes to opioid medicine, developing a personalised management plan using a shared decision making approach, signposting to relevant self-management/self-care information resources). The eCRFs will be analysed at the end of the study to assess engagement with the intervention, intervention uptake, delivery, and to identify any further training requirements ahead of a main cluster RCT.

### Acceptability Questionnaire

All participants who attended the clinical pharmacist appointment will be mailed a short survey (known as the Acceptability Questionnaire) about their experiences of the consultation, which will supplement the qualitative data. This short survey will have a total of 12 questions from two existing measures: a modified version of the treatment acceptability and credibility measure and the Theoretical Framework of Acceptability (TFA) questionnaire. The modified acceptability and credibility measure has been used in previous similar studies. The measure includes 4 items, (scored on a 0-10 scale) and will assess (1) how logical the PROMPPT Intervention seems to participants, (2) how confident participants are that it will be successful in helping them (3) how confident participants would be in recommending it to a friend and (4) how satisfied they were with the intervention overall.

The TFA questionnaire comprises 8 items (scored on a 0-5 scale) . The first is a global acceptability question and the remaining 7 (items 2-8) represent key constructs of

acceptability relating to healthcare interventions (affective attitude, burden, intervention coherence, ethicality, perceived expectations, opportunity cost, and self-efficacy).

#### Semi-structured interviews

Patient participants will be interviewed after attending at least one appointment with the clinical pharmacist. The interviews will be based on semi-structured topic guides developed in association with our PPIE group and will include questions informed by our programme theories regarding behaviour change, implementation and acceptability. Topic guides will be refined during data collection to allow any emerging issues to be explored. A similar process will be followed for the clinician participants whereby they will be interviewed once they have experience of PROMPPT intervention delivery.

We expect that up to 15 patients (sampled from across the 4 participating practices) and approximately 8 clinicians, n=4 GPs and n=4 clinical pharmacists (one of each from each participating practice) will be sufficient to attain rich data. We will cover similar topics with all interviewees to ensure we can compare their responses, while at the same time enabling them to reflect on their specific expectations, understandings and experiences. All interviews will be conducted by an experienced qualitative researcher. With the participants' consent, interviews will be audio recorded. The interviews will be securely sent to a professional transcription company (The Transcription Company UK) who operate under the terms of a confidentiality agreement and who have an existing contract with Keele CTU. Transcripts will be transcribed verbatim. Transcripts will be anonymised by members of the research team ahead of analysis.

### 5.3.3 Medical Record Review (MRR)

Full general practice medical records of consenting participants will be accessed and extracted and securely transferred to the study team to obtain information on consultations, prescriptions and associated aspects in the medical record, for the duration of the study requirements.

# Table 1. Schedule of Data Collection

# Table 1. Schedule of Data Collection

	Time point										
Outcome measure	Baseline	PROMPPT consultation	Post PROMPPT consultation	Follow-up 3 months from baseline							
Self-reported questionnaires				1							
Demographics (sex, date of birth)				Ø							
Chronic pain duration (in years, single question)	Ø										
Pain severity: Brief Pain Inventory (BPI) pain subscale 	Ø			Ø							
Pain-related interference: BPI pain interference subscale 	Ø			Ø							
Opioid medicines use, expressed as average daily morphine equivalent dose (MED)	Ø			Ø							
Opioid-related pain medication side-effects checklist	Ø			Ø							
Other (non-opioid) pain medicines use (drug name(s), dose(s), frequency)	Ø			Ø							
Pain Self-Efficacy Questionnaire (PSEQ) 	Ø			Ø							
Health-related quality of life (EQ-5D-5L) 	Ø			Ø							
Healthcare resource use (chronic pain and opioid side-effect related)				Ø							
Work (work status, occupation, time off work, Single-Item Presenteeism Question from the Work Productivity and Activity Impairment Questionnaire 				Ø							
Process measures		'		1							
PROMPPT intervention case report form		☑									
Fidelity checklist using observed/audio-recorded consultations		Ø									
Acceptability Questionnaire 57,58			Ø								
Semi-structured interviews with patient participants			Ø								
Semi-structured interviews with clinical pharmacists			Ø								
Semi-structured interviews with GPs											

#### 5.4 Withdrawal Criteria

Participants are free to withdraw from the study at any time. Keele CTU will make every effort to ensure that the specific wishes of any participant who wishes to withdraw consent for further involvement in the study are defined and documented.

Participants who wish to withdraw from the study will have the option to still attend for initial and/or follow-up PROMPPT consultations with the practice clinical pharmacist if they wish.

# 5.5 End of Study

The end of the study is defined as the point at which data collection is complete and the study database is locked. All CRFs, audio files and transcripts will have been received by the data management team at Keele CTU and any data queries will have been resolved. The Chief Investigator will notify the REC of the end of the study within 90 days of study completion.

#### 6 STATISTICS AND DATA ANALYSIS

# 6.1. Sample size

Based on data from our regional anonymised primary care database (Consultations in Primary Care Archive (CiPCA)), we expect to identify around 270 patients with persistent pain prescribed long-term opioids per average sized practice of around 5000-6000 patients. Assuming GPs exclude 30% of patients identified according to study exclusion criteria and assuming that a minimum of 25% of those contacted consent to participate and return a baseline questionnaire, we estimate a mean of at least 47 eligible patients per practice will consent to participate.

A sample of 80 eligible participants from across 4 practices in 2 regional centres is therefore feasible and will allow us to estimate the overall consent rate with precision of at least  $\pm 10\%$ . Similarly, if the 3-month follow-up rate is around 75%, this estimate will have precision of around  $\pm 10\%$ .

# 6.2 Quantitative data analysis

Analysis of the quantitative data from the study will be exploratory and used to inform the design of a future main trial

#### 6.2.1 Recruitment and retention rates

A CONSORT flow diagram will be produced and used to estimate the following proportions:

- % (out of all GP registered patients) identified to be screened by GP
- % eligible (out of all GP registered patients) to be mailed a study invitation
- % returning a baseline questionnaire (out of those mailed a study invitation)
- % of participants attending the initial PROMPPT consultation with the clinical pharmacist (out of those who returned the baseline questionnaire)
- % of participants who have at least one follow-up appointment scheduled (out of those who attend the initial consultation)

- % of participants who fail to attend one or more scheduled follow-up appointments (out of those who are scheduled a follow-up following the initial consultation)
- % of participants returning a 3-month follow-up questionnaire (out of those consenting to complete questionnaires at baseline)

These estimates will be used to review the feasibility of recruitment and follow-up for a main trial.

# 6.2.2 Baseline and follow-up questionnaire completion

Missing data rates will be calculated for each outcome measure in the baseline and follow-up self-report questionnaires at each data collection time-point (baseline and 3-month). Outcomes with a poor completion rate will be identified and used to inform if any changes are needed to the outcome measures used as data collection tools in a main trial design.

### 6.2.3 Participant characteristics

Participants baseline characteristics will be described (using means, standard deviations, medians, interquartile range, numbers and percentages as appropriate) to characterise the sample and also highlight any potential areas of selection bias that could be minimised in a main trial design. Participants' baseline characteristics will be explored in the following subgroups, however, between-group differences will not be tested for statistical significance due to small sample size:

- Eligible patients mailed a study invitation (date of birth, sex and postcode deprivation only)
- Eligible patients consenting to participate and returning a baseline questionnaire
- Participants returning a 3-month follow-up questionnaire

# 6.2.4 Intervention delivery template

The intervention delivery template will be reviewed for each participant and the proportion of times that each component of the intervention was used will be reported. A judgement will also be made as to whether the patient received the intervention as per-protocol and whether the patient attended all scheduled follow-up appointments. The proportion of patients being treated per-protocol will then be calculated out of all participants who attended the first appointment with the clinical pharmacist.

### 6.2.5 Feasibility of primary outcome data collection for a main trial

The proposed co-primary outcomes for a main trial are Brief Pain Inventory (total score combining pain severity and pain interference subscales) and opioid use, expressed as average daily morphine equivalent dose.

Average daily morphine equivalent dose (MED) will be calculated at baseline and 3-month follow-up using data from the self-report questionnaires and prescribing data from linked medical records. Correspondence in MED between the two data sources will be explored by calculating individual differences in MED between self-report and MRR data at each time point and plotting the resulting distributions.

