	
 
Proportion of participants returning a 3-month follow-up questionnaire (out of those consenting to complete questionnaires at baseline).
 

2. Completeness of data collection.	Missing data rates will be calculated for each outcome measure in the baseline and follow-up self-report questionnaires at each data collection time-point (baseline and 3-month).
3. Fidelity of intervention delivery per protocol.	
 
Proportion of times that use of each intervention component is recorded in intervention case report forms (CRFs).
 
Proportion of patients being treated perprotocol (out of all patients who attended the initial clinical pharmacist appointment).
 
Findings from qualitative analysis of observed/audio-recorded consultations.
 

Suitability of a self-reported pain medicines use questionnaire to calculate mean daily morphine equivalent dose.	
 
Completeness of response to pain medicines use questionnaire.
 
Comparison of average daily morphine equivalent dose (MED) calculated using data from self-report questionnaires with MED calculated using prescription data from electronic medical records at baseline and 3-month follow-up.
 

5. Suitability of the health resource use questionnaire for use in a future health economic evaluation.	Rate and completeness of response to healthcare resource use and productivity questionnaire.
6. Barriers to and facilitators of successful delivery of the intervention.	
 
Findings from observed/audio-recorded consultations.
 
Findings from interviews with patients, clinical pharmacists and GPs.
 

 
The acceptability and credibility of the intervention to patients.
 
	
 
Responses to the Acceptability Questionnaire.
 
Findings from interviews with patients.
 

8. Acceptability of the intervention and training to clinical pharmacists and GPs, and the feasibility of delivering the intervention in general practice.	Findings from interviews with clinical pharmacists and GPs.

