# 3.1 Primary objectives

- Determine the availability and recruitment of eligible patients, the proportion scheduling and attending clinical pharmacist appointments and rates of retention at 3-month followup;
- 2. Determine the completeness of data collection;
- 3. Determine the fidelity of intervention delivery per protocol;
- 4. Determine the suitability of a self-reported pain medicines questionnaire and electronic medical records to calculate mean daily morphine equivalent dose;
- 5. Determine the suitability of the health resource use questionnaire for use in a future health economic evaluation;
- 6. Determine the potential barriers to and facilitators of successful delivery of the intervention:
- 7. Determine the acceptability and credibility of the intervention to patients;
- 8. Determine the acceptability of the intervention and training to Clinical Pharmacists and GPs, and the feasibility of delivering the intervention in general practice.

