### 4.3.2 Individual patient participants

#### Inclusion criteria

- (1) Adult patients aged ≥18 years who are:
- (2) Prescribed any opioid analgesic (defined as any opioid or opioid/paracetamol combination analgesic from sections 4.7.2 and 4.7.1 British National Formulary (BNF) for chronic non-cancer pain continuously for ≥6 months, with a prescription issued within the previous 2 months.

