#### 6.2.6 Health economic evaluation

A formal health economic evaluation will not be conducted in this feasibility study.

To assess the feasibility of the proposed health economic evaluation for the main trial, we will assess the level of completion of the EQ-5D-5L questionnaire at baseline and 3 months, and the level of completion and suitability of the patient resource use questionnaire at 3 months.

Overall response rates for each questionnaire will be calculated. Within questionnaire completion rates will also be calculated in order to assess the level of completion of specific questions. Assessment of appropriateness of completion will also be undertaken, with questions to be refined as necessary.

Data on opioid prescriptions and use will be available from patient self-report questionnaires and medical record review. This will allow comparison of the two data sources to determine the final method of data collection on opioids for the economic evaluation within the definitive trial.

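### Plotting raw differences alone hides any dependence of self-report versus record MED agreement on dose, and completeness is planned for the questionnaire only

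*Protocol*

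**What the plan says.** Objective 4 in Protocol 3.1 reads: "Determine the suitability of a self-reported pain medicines questionnaire and electronic medical records to calculate mean daily morphine equivalent dose". The Study Summary words the same objective for the questionnaire alone, so 3.1 is the wider statement.

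Section 6.2.5 proposes daily MED as one of two co-primary outcomes for the main trial. It calculates MED from each source at baseline and 3 months, then explores correspondence by "calculating individual differences in MED between self-report and MRR data at each time point and plotting the resulting distributions". It names no agreement statistic, no plot against dose and no comparison of change from baseline.

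On the data behind each source:

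- Section 5.3.1 (Clinical outcome measures) uses "participant self-reported data about opioid use over the preceding 4 weeks, and using prescribing data from electronic medical records". Only the self-report side has a stated period.
- Section 5.3.3 extracts full general practice records "for the duration of the study requirements".
- Section 5.1.2 groups the patients identified by opioid strength: weak, intermediate or strong.

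On completeness, the Study Summary lists "Completeness of response to pain medicines use questionnaire", and 6.2.2 gives missing-data rates for the measures in the self-report questionnaires. On the decision, 6.2.6 says of the opioid data: "This will allow comparison of the two data sources to determine the final method of data collection on opioids", for the economic evaluation in the definitive trial.

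**The concern.** A paired difference in mg means different things at different doses. The same gap can be a gross error in a patient on a weak opioid and a trivial one in a patient on a high dose of a strong opioid. A plot of the distribution of differences keeps the size of each gap and loses the dose at which it arose. Bias that changes with dose, or spread that widens with dose, is therefore not visible in the stated output.

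Two related gaps follow. Differences taken separately at each time point do not show whether the two sources agree on how much a patient's dose changed. A difference also needs both sources, so it says nothing about participants for whom only the record is available. Loss of questionnaires is planned to be measured, but the share of participants whose record yields a usable MED is not.

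At stake is how informative the study is on objective 4, and hence on the choice of opioid data source for later work.

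**Working it through.** **1. Number of pairs.** Section 6.1 gives 80 participants and a 3-month follow-up rate of around 75%, with precision of around ±10%. Check: 1.96 × √(0.75 × 0.25 / 80) = 0.095, so ±9.5%, which reproduces the stated figure. There are at most 80 baseline pairs and about 80 × 0.75 = 60 at 3 months, fewer if some participants decline record access. No figure is stated for the MED comparison itself.

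**2. What the stated output keeps.** Let d = self-report MED − record MED. The distribution of d gives the mean difference, its SD and outliers. Limits of agreement, mean ± 1.96 SD, could be read from it. It does not carry the patient's mean dose.

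**3. Size if disagreement is proportional to dose (assumption).** The protocol gives no MED distribution. Assume log-normal MED with median 30 mg and log-SD σ = 1. Take one source as the dose and let the other differ by a factor with log-SD 0.3.

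- Ratio limits: exp(±1.96 × 0.3) = 0.56 to 1.80 at every dose.
- The upper limit in mg above the dose: 15 × 0.80 = 12 mg at 15 mg, and 90 × 0.80 = 72 mg at 90 mg.
- Root mean square difference: √[(e^0.18 − 2e^0.045 + 1) × 30² × e²] = √(0.1052 × 6650) = 26 mg.
- By simulation, the SD of d is 26 mg overall, 3 mg below 15 mg and 64 mg above 90 mg.

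The share of patients above 90 mg is 1 − Φ(ln 3 / σ). Their share of the squared disagreement is 1 − Φ(ln 3 / σ − 2σ), whatever the size of the proportional error:

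| Assumed σ | Patients above 90 mg | Their share of squared disagreement |
|---|---|---|
| 0.5 | 1.4% | 12% |
| 1.0 | 14% (about 11 of 80) | 82% |
| 1.2 | 18% | 93% |

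If disagreement were instead constant in mg, its spread would be the same at every dose. The raw scale would then be the right one and the ratio scale would mislead. Which case applies is an empirical question, and the stated plot cannot answer it.

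**4. Precision of limits of agreement.** The 95% CI half-width of each limit is t × √[1/n + 1.96² / (2(n − 1))], in SDs of the differences. It is 0.38 SD with 80 pairs and 0.44 SD with 60. For the mean difference it is 0.22 and 0.26 SD. In the example on the log scale with 60 pairs, 0.44 × 0.3 = 0.13, so the upper limit of 1.80 has a CI of about 1.58 to 2.06.

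**5. Completeness, side by side.**

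| Planned measure | Questionnaire | Records |
|---|---|---|
| Completeness of pain medicines questionnaire (Study Summary) | yes | no |
| Missing-data rates (6.2.2) | yes | no |
| 3-month return rate (6.2.1) | yes | no |
| Paired differences (6.2.5) | only where both exist | only where both exist |

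At 75% return, about 80 − 60 = 20 participants have no 3-month pair. Those who gave record access could still have a record MED, but no planned measure counts them.

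**The case against.** The best reply is that much of this is analysis-plan detail. The protocol states nothing false here. Individual differences are the raw material of a Bland-Altman analysis, and the scale, axes and handling of zeros are commonly settled later in an analysis plan that is not shown. Section 6.2 calls the quantitative analysis exploratory, and 6.5 has no MED criterion. Questionnaire loss, against which the advantage of records would be judged, is measured. Most of this stands, and it limits the weight of the point. It does not remove it, because 6.2.5 does name its method for a primary objective, and that method leaves out dose.

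Three stronger readings are tempting, and the protocol does not support them.

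- *The two sources cover mismatched periods.* Self-report covers 4 weeks, and eligibility requires continuous prescribing "with a prescription issued within the previous 2 months". But no record period is stated, so no mismatch is stated either. The 2 months is a recency limit, not an issue interval.
- *Record MED would be zero or double in stable patients.* This needs 56-day issues, a 28-day record window and a dose computed as amount issued divided by 28. None of these is in the protocol. With 28-day issues the same calculation gives no error. Nor is a long look-back an obvious cure: at 3 months it would mix doses from before and after the pharmacist review.
- *The plan cannot show which source suits the co-primary outcome.* Bias, spread and questionnaire completeness all bear on that. The explicit choice of source in 6.2.6 is for the economic evaluation, and for the proposed co-primary outcome 6.2.5 only explores correspondence.

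**Conclusion.** The point holds in limited form: cheap improvement. The agreement output stated in 6.2.5 shows average bias and spread but cannot reveal dose-dependent disagreement, does not examine agreement in change, and is not matched by any completeness measure for records, although objective 4 in 3.1 includes them.

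The size depends on assumptions. If disagreement is proportional to dose, patients above 90 mg contribute 12% to 93% of the squared disagreement as the assumed log-SD of MED runs from 0.5 to 1.2, and 82% at 1.0. If disagreement is constant in mg, the raw plot loses nothing on this score. No stated figure is wrong, and no progression decision turns on this analysis. The missing record period is a detail to supply, not a demonstrated misalignment.

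**What to change.** In 6.2.5, or in the analysis plan with a reference from 6.2.5:

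- Plot the difference against the mean of the two sources (Bland-Altman), with limits of agreement and their confidence intervals on both the raw scale and the log (ratio) scale.
- Tabulate patients with zero MED from either source separately, since a ratio is undefined for them.
- Do this at baseline, at 3 months and for change from baseline.
- Report the percentage with a calculable MED from each source at each time point, among all who consent to record review, including those who do not return the 3-month questionnaire.
- State the rule and anchor date for record MED, so that it reflects the same 4 weeks as self-report.

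The cost is a little more analysis of data already being extracted. With about 60 to 80 pairs the limits will be imprecise (±0.38 to ±0.44 SD), so they should be read with their intervals and not used as a pass or fail test.
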